## **6 TRIAL OBJECTIVES AND PURPOSE**

### **6.1 Primary Hypothesis**

The primary hypothesis in this pilot study of elderly thoracic surgical patients undergoing procedures involving SLV is that there will be a measurable and significant clinical benefit (as assessed by a broad range of postoperative clinical outcome measures) to the subjects randomized to the intervention cohort (open bi-frontal NIRS based cerebral oximetry monitoring with a standardized intervention protocol) vs. the control cohort (blinded bi-frontal NIRS based cerebral oximetry monitoring).

### **6.2 Primary Objective**

The primary objective of this pilot study is to identify the most relevant clinical outcome variables which significantly diverge as a result of being randomized to the intervention cohort vs. the control cohort so that a larger, multicenter, prospective, randomized controlled clinical trial can be designed to further test the primary hypothesis as stated in the preceding section. The subsequent larger, multicenter trial will be conducted to definitively demonstrate the ability of INVOS® 5100 guided NIRS-based bi-frontal monitoring to improve clinical outcomes in this surgical patient group and potentially establish a new U.S. Food and Drug Administration cleared indication for this monitoring modality.

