**Criteria for Evaluation:**

A large number of intraoperative and postoperative clinical variables that include cerebral oximetry, pulse oximetry, blood pressure, a composite outcome measure and clinical variables representing organ function will be assessed with the primary endpoint being the determination of which clinical variables are improved, if any, as a result of being randomized to open NIRS data monitoring with a predefined desaturation intervention algorithm guideline. The Mini Mental Status exam and Confusion Assessment Method test will be used to determine if any measured clinical variables have an effect upon neuropsychological outcomes. The frequency and effectiveness of the various cerebral desaturation mitigating interventions will be assessed in the intervention cohort.

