### **Study Rationale**

There are presently two prospective, randomized controlled trials which strongly support the notion that these devices improve perioperative clinical outcomes in surgical patients as well as a large number of observational studies which strengthen the association of the use these devices to improved outcomes. (Murkin JM et al, Cassati A et al, Goldman S et al, Heringlake M et al, Schoen J et al) However, there is only one published observational study performed to date involving the use of NIRS-based regional cerebral oximetry of thoracic surgical patients undergoing SLV. That study only assessed the association of NIRS-based cerebral oximetry to postoperative neurocognitive dysfunction and did find a positive relationship between observed cerebral oximetry data and postoperative cognitive dysfunction (i.e. 29% of patients had significantly decreased Mini Mental Status Exam scores at 3 hours postoperatively and a ↓rSO2 <65% for even just 5 minutes was associated with ↑OR 2.03 [95% CI: 0.74 – 5.59]) for developing early neurocognitive dysfunction. (Tang L)

Elderly thoracic surgical patients undergoing SLV related procedures were not included in any of the prospective randomized controlled trials and only the single, small observational study referenced above assessing postoperative neurocognitive dysfunction exists to test the hypothesis that NIRS based bifrontal cerebral monitoring has the potential to affect any clinical outcome in this subpopulation of surgical patients. Further, NIRS based bi-frontal cerebral monitoring is not accepted as a standard of care in thoracic surgical patients which permits the employment of randomized, controlled testing methodology in this patient population.

The establishment of cause and effect in clinical medicine is largely dictated by the conduct of multicenter, prospective, randomized controlled trials. This pilot study is intended to define the optimal clinical endpoints and statistical design needed to establish the potential benefits of NIRS based bi-frontal regional cerebral oximetry monitoring in elderly thoracic surgical patients undergoing procedures involving SLV.

This pilot study involves the collection not only of cerebral oximetry data but also of blood pressure and pulse oximetry data as well as a number of clinically relevant outcome measures that can reflect the adequacy of organ protection during the intraoperative and immediate postoperative period. Having serial

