#### **6.4 Exploratory Objectives**

Exploratory objectives will include performing all possible comparisons of the two groups based upon all collected perioperative variables to examine the potentially significant relationships between the collected clinical variables representing surrogates of organ perfusion/function and cerebral oximetry desaturations (AUCrSO2). The following exploratory endpoints will be assessed:

- Logistic regression analysis to determine the most relevant AUCrSO2 desaturation value(s) associated with any detrimental clinical outcome(s) monitored in this study
- Logistic regression analysis to determine the most relevant AUC blood pressure values associated with any detrimental clinical outcome(s) monitored in this study
- Comparison of baseline rSO2 values (room air and oxygen supplemented) to all collected clinical variables to assess for possibly significant associations

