## **Schematic Diagram of Trial Design**

## 7.4 Study Variables

### 7.4.1 Primary Endpoints

The relationship between the observed cerebral oximetry data and a number of predefined intraoperative and postoperative clinical variables will serve as the primary endpoints of this trial. The clinical variables will include the following intraoperative and postoperative (PACU or initial 12 hours of the ICU stay) parameters:

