### 11.3 Protocol Assessments and Procedures – Intraoperative and Immediate Postoperative Period

#### 11.3.1 General Intraoperative and Immediate Postoperative Period Description

During this period a host of clinical variables will be collected on each subject that will serve as the primary endpoints of this pilot study.

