## **15 STATISTICAL PLAN**

All collected data in the case report form will be transferred into a customized electronic database upon completion of the study for the purpose of facilitating statistical analysis.

Preoperative demographics and clinical variables will be compared in the two groups to assess for significant differences using the independent t-test. Differences in the observed clinical data between groups will be determined with the Wilcoxon rank-sum test. Stepwise, forward, multivariable logistic regression analysis will be performed to assess for relationships between cerebral desaturations and any of the measured clinical variables with a p value < 0.05 being considered significant.

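### Section 6.2 chooses the next trial's endpoints by between-arm significance from a long unranked list at 50 per arm, a screen that can pick chance findings, misses modest real effects and overstates small to moderate ones.

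*Combined protocol and SAP*

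**What the plan says.** - Section 6.1 states the hypothesis that "there will be a measurable and significant clinical benefit (as assessed by a broad range of postoperative clinical outcome measures". It names no single measure.
- Section 6.2 sets the primary objective: to "identify the most relevant clinical outcome variables which significantly diverge as a result of being randomized to the intervention cohort" so that a larger trial can be designed. How relevance is to be judged is not defined.
- The Study Rationale in section 5 gives the purpose: "This pilot study is intended to define the optimal clinical endpoints and statistical design".
- The synopsis (Criteria for Evaluation) agrees, with "the primary endpoint being the determination of which clinical variables are improved, if any".
- Section 11.3.1 gives the collected variables primary status: "a host of clinical variables will be collected on each subject that will serve as the primary endpoints of this pilot study". Section 7.4.1 contains the lists, but defines the endpoints differently: "The relationship between the observed cerebral oximetry data and a number of predefined intraoperative and postoperative clinical variables will serve as the primary endpoints".
- Section 6.4 adds, as exploratory work, "performing all possible comparisons of the two groups based upon all collected perioperative variables".
- Section 15 gives the between-arm method: "Differences in the observed clinical data between groups will be determined with the Wilcoxon rank-sum test". The only significance level in the section, 0.05, appears in the next sentence and is attached to the stepwise logistic regression.

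The plan has no ranking of endpoints, no multiplicity rule and no power or precision statement. It has no rule for turning a significant variable into the next trial's endpoint or planning effect.

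**The concern.** A main product of this pilot is a choice: which endpoint the multicentre trial should use. Under 6.2, statistical significance makes that choice. With 50 per arm and many candidates, such a filter has three weaknesses. Some variables pass by chance. Real effects of modest size usually fail. Those that pass do so partly because chance pushed the estimate up.

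The list also mixes outcomes with items that cannot measure patient benefit. Surgical procedure performed, epidural use and time on single lung ventilation describe the case. Fluids and vasoactive drugs are among the responses that section 10.3 itself describes for a desaturation, so a difference there may only show that the algorithm was followed.

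At stake is a definitive trial built on a poorly chosen endpoint, or planned from an optimistic effect. Section 6.1 could also be called supported by one isolated result.

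**Working it through.** The documents give no power, effect size, SD or event rate, so there is no stated figure to reproduce. The effect sizes and event rates below are assumptions.

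**Inputs.** 100 subjects randomised 1:1, so 50 per arm (section 7.1). Rank-sum test (section 15). Two-sided 0.05, inferred, because section 15 writes that level for the regression.

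**Count from section 7.4.1**, with each AUC cut-off, each baseline and each other bullet counted once:
- rSO2 AUCs per period: 8 relative cut-offs × 2 baselines + 9 absolute cut-offs = 25
- Blood pressure AUCs per period: 3 pressures × 3 forms = 9
- SpO2 AUCs per period: 6
- Other bullets: 16 intraoperative (including the glucose AUC) and 28 postoperative (including the composite)
- Intraoperative 25 + 9 + 6 + 16 = 56; postoperative 25 + 9 + 6 + 28 = 68; total 124, of which 2 × 40 = 80 are rSO2, pressure or SpO2 AUCs

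The hypothesis concerns postoperative clinical outcomes, so the 28 postoperative bullets are the fairest base.

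**Chance findings with no true effect.**
- Expected number among 28, whatever their correlation: 28 × 0.05 = 1.4; in the benefit direction, 28 × 0.025 = 0.7
- At least one in the benefit direction: 1 − 0.975^28 = 0.51 if independent; 1 − 0.975^15 = 0.32 if they act like 15 tests
- At least one in either direction: 1 − 0.95^28 = 0.76; 1 − 0.95^15 = 0.54
- On the full list, 124 × 0.05 = 6.2

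These are upper figures. Exact enumeration of the uncorrected rank-sum test on a binary outcome at 50 per arm gives a true level of 4.3% at an assumed 5% event rate, 1.3% at 2% and 0.2% at 1%.

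**Selection and inflation.** Simulation with normal data, rank-sum test and 50 per arm. Inflation is the mean selected |d| divided by the true d. The last column is 1 ÷ inflation², the share of the required patients that a trial sized on the selected estimate would enrol.

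| True d | Selected | Inflation | Share of patients needed |
|---|---|---|---|
| 0.2 | 16% | 2.5 | 1/2.5² = 16% |
| 0.3 | 30% | 1.8 | 1/1.8² = 31% |
| 0.5 | 68% | 1.2 | 1/1.2² = 69% |
| 0.8 | 97% | 1.02 | 1/1.02² = 96% |

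For binary outcomes, exact enumeration selects a true 20% v 10% risk 28% of the time, and 10% v 5% 14% of the time. ICU length of stay would do worse than the table, since section 7.4.1.2 expects at least 10-20 evaluable subjects, or about 5-10 per arm at that number.

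**Share of significant results due to chance.** If k of the 28 items are truly affected, the share is (28 − k) × 0.05 ÷ [(28 − k) × 0.05 + k × selection rate].
- k = 2: 1.30/(1.30 + 0.60) = 68% at d = 0.3; 1.30/(1.30 + 1.36) = 49% at d = 0.5
- k = 5: 1.15/(1.15 + 1.50) = 43% at d = 0.3; 1.15/(1.15 + 3.40) = 25% at d = 0.5

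Counting only benefit-direction results (0.025 in place of 0.05) gives 52%, 32%, 28% and 14%.

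**Would a correction suffice?** Bonferroni over 124 needs p < 0.05/124 = 0.0004, which leaves about 15% power at d = 0.5. The selection rule itself has to change.

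**The case against.** The strongest reply is that this is a declared pilot. A larger trial is to test the hypothesis further, section 6.4 labels the all-comparisons work exploratory, and four secondary objectives do not depend on the screen. That is fair, and it limits the harm: no false efficacy claim follows automatically. But exploratory status excuses unadjusted p values; it does not make them a good rule for choosing endpoints, and 6.2 makes that choice the primary objective.

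Other points stand and limit the claim:
- A reader might take all 124 variables as candidates. Section 6.2 speaks of relevant clinical outcomes and 6.1 of postoperative ones. Section 7.4.1 also ties its list to oximetry relationships, not to arm differences. Fifty of the 124 are rSO2 AUCs, which the intervention targets and which may truly differ.
- A reader might quote the 76% (or 54%) chance of a false positive. The hypothesis is benefit and the synopsis speaks of improvement, so 51% (or 32%) is the relevant figure.
- A reader might infer that nothing below an observed |d| of about 0.40 can be significant. That is a t-test cut-off; in simulation at d = 0.2, about 12% of significant rank-sum results fall below it.
- Relevance is named as a filter alongside significance. It is undefined, so it does not constrain the choice.

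**Conclusion.** The concern holds in a limited form. The plan selects endpoints on between-arm significance from a long unranked list, with 50 per arm and nothing to discount chance. On the 28 postoperative items, a null intervention would yield about 0.7 benefit-direction findings on average, and at least one with probability up to about 51% (32% for 15 effective tests). True effects of d = 0.2 to 0.3 would be missed in about 70-84% of trials and overstated about 1.8- to 2.5-fold when found.

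Two stronger readings are tempting but unsupported. One is that the screen mostly passes chance findings: the share runs from 68% to 14% across the cases shown, and the documents do not settle which applies. The other is that it exaggerates every real effect: inflation is 1.2-fold at d = 0.5 and about 2% at d = 0.8. Nor do the documents say that the next trial will be sized on the observed effect, so an undersized trial is a risk to rule out, not a stated plan.

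These figures assume two-sided 5% rank-sum tests, the illustrative effects and event rates given, and normal data for the continuous case. This should be fixed, but in a declared pilot with a confirmatory trial to follow it does not undermine the study.

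**What to change.** In sections 6.1, 6.2 and 15:

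1. Before any between-arm analysis, fix a short list of postoperative patient outcomes as candidate endpoints. Report the AUCs, procedure, epidural use, single lung ventilation time, fluids and algorithm drugs as process or mechanism description. Align the primary-endpoint definition in 7.4.1 with 6.2.
2. Replace significance as the selection criterion with patient importance, completeness of data, control event rate or SD, and the estimated effect with its confidence interval. Label p values exploratory, and state which level and sidedness apply to the rank-sum comparisons.
3. State that no single p < 0.05 establishes the section 6.1 hypothesis.
4. State that the next trial will be sized on a clinically important difference, using the pilot's SD or control rate, and not on the observed effect of a selected outcome.

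The length of the short list, and whether to add adjusted p values for it, are matters of preference. The changes are to wording only and need no new data. The cost is that the pilot can no longer claim significant benefit from an isolated p value.

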### **6.3 Secondary Objectives**

Secondary objectives of this pilot study include the following:

- 1) Assess the frequency of cerebral desaturations in both the intervention and control cohorts by examining both the total number of patients experiencing any cerebral desaturation as well as the total number of events among patients experiencing any cerebral desaturation (of at least 5% below baseline and progressively larger desaturations). These analyses will be conducted on the entire study population as well as upon each cohort. The Area Under the Curve (AUC) analysis

technique [incremental desaturation categories will be assessed based upon 5 to 50% decreases, measured in 5% increments, from established room air baseline as well as oxygen supplemented pre-incision baselines as well as desaturations below absolute measured rSO2 values] will be employed to conduct these analyses.

- 2) Assess the frequency of adverse clinical events and serious adverse events overall and in each cohort.
- 3) Perform a comprehensive assessment of the frequency and efficacy of predefined rSO2 desaturation mitigation interventions and their collective ability to affect the observed cerebral oximetry values.
- 4) Assess the interventional cohort's preoperative demographics and collected covariates for association with the ease or difficulty of mitigating observed cerebral desaturation events.

#### **6.4 Exploratory Objectives**

Exploratory objectives will include performing all possible comparisons of the two groups based upon all collected perioperative variables to examine the potentially significant relationships between the collected clinical variables representing surrogates of organ perfusion/function and cerebral oximetry desaturations (AUCrSO2). The following exploratory endpoints will be assessed:

- Logistic regression analysis to determine the most relevant AUCrSO2 desaturation value(s) associated with any detrimental clinical outcome(s) monitored in this study
- Logistic regression analysis to determine the most relevant AUC blood pressure values associated with any detrimental clinical outcome(s) monitored in this study
- Comparison of baseline rSO2 values (room air and oxygen supplemented) to all collected clinical variables to assess for possibly significant associations

### **7 STUDY DESIGN**

#### **7.1 Study Design**

This study is a single center (University Hospitals Case Medical Center), prospective, randomized, controlled pilot study of elderly thoracic surgical patients undergoing procedures involving the use of SLV. A total of 100 eligible subjects will be randomized in a balanced fashion (1:1) to either the control cohort that will have electronically blinded bi-frontal cerebral oximetry monitoring or the intervention cohort that will have open bi-frontal cerebral oximetry monitoring with a predefined intervention protocol for observed desaturations of greater than 20% of established oxygen supplemented baseline values (see Appendix C). Both the control and intervention groups will have baseline NIRS data obtained in an unblinded fashion. The study will be divided into four separate periods that include screening, baseline acquisition, intraoperative and immediate postoperative and the postoperative follow up period.

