### 7.2.2 Baseline Acquisition Period

Following randomization using an envelope randomization technique to either the control or intervention cohort enrolled subjects will undergo baseline testing with the MMSE and CAM assessment tools. Subsequently all subjects will have acquisition of bifrontal NIRS cerebral oximetric readings on both room air and with 100% oxygen supplementation. The control group and the intervention group will have open NIRS baseline data collection. This will allow all enrolled subjects to demonstrate that a set of baseline rSO2 values can be obtained and thus reduce the probability of unreadable outliers (i.e. subjects with anomalously located frontal sinuses) being studied in the control group. The baseline acquisition will occur in the operating room just prior to anesthesia induction.

[figure not shown]

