### **10.2 Control Group**

The control group will have both room air and oxygen supplemented baselines obtained in an antecedent fashion to establish that they can produce reliable bilateral cerebral oximetry readings. Because it is known that the device may not be able to produce a valid reading in some individuals with pigmented skin or aberrantly located frontal sinuses this step is necessary to insure that all subjects in the control group will produce useful NIRS data. Once the baseline values have been recorded the cerebral oximetry will be monitored in an electronically blinded manner. Specifically, the device will capture data but neither the current values nor the trend will be displayed on the device's display console. The use of this modified version of the device will help to reduce investigator bias that might be introduced if a blinder were affixed to the display console. The baseline values will be obtained prior to the induction of general anesthesia.

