#### 11.2.4.2 Oxygen Supplemented Baseline rSO2

Once that subject has been breathing 100% oxygen for a full two minutes as assessed by the research assistant's timer the oxygen supplemented rSO2 baselines will be recorded when the NIRS data is stable bilaterally. The time of this event will be recorded on the study data collection tool.

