11.2.4.3 Blinding of Control Group

After recording the two sets of baseline rSO2 data the subjects that have been randomized to the control group will have their rSO2 data electronically blinded via activation of a device modification that will have been previously performed by the device manufacturer.

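### Control-arm baseline rSO2 values are shown openly in the operating room, and nothing keeps them from the treating anesthesia team: a modest, avoidable performance-bias risk

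*Combined protocol and SAP*

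**What the plan says.** Section 7.1 states: "Both the control and intervention groups will have baseline NIRS data obtained in an unblinded fashion". Section 7.2.2 repeats the arrangement ("The control group and the intervention group will have open NIRS baseline data collection") and fixes the place and time: "The baseline acquisition will occur in the operating room just prior to anesthesia induction".

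The reason is given openly. Section 10.2 says that baselines are taken in controls to "establish that they can produce reliable bilateral cerebral oximetry readings". Skin pigmentation or sinus position can defeat the sensor, so "this step is necessary to insure that all subjects in the control group will produce useful NIRS data". Section 7.2.2 gives the same kind of reason.

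Section 11.2.4 sets the order. The bilateral room-air values come first, before preoxygenation. The oxygen-supplemented values follow two minutes on 100% oxygen, "as assessed by the research assistant's timer". Blinding of a control comes only then: "After recording the two sets of baseline" values (11.2.4.3). From that moment sections 8.6 and 10.2 hide both the current reading and the trend.

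Sections 11.2.4.1 and 11.2.4.2 enter the time of each baseline on the study data collection tool. No section says who may look at the console while baselines are taken, or that the anesthesia clinicians may not.

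**The concern.** The control arm is meant to be managed without sight of cerebral oximetry. Section 8.6 goes as far as a manufacturer's modification of the device to achieve this, and section 11.3.2 describes capture of rSO2 in the anesthesia computer system only for the intervention group. Yet two bilateral sets of values are on display shortly before that protection starts, at a time when the anesthesia team would be expected at the patient's side.

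A clinician who notices a low baseline, or a poor response to oxygen, could manage a control differently. The measures listed in section 10.3 (arterial pressure, carbon dioxide, inspired oxygen) include ordinary anesthetic steps that are open to any clinician. If some controls receive such care because of what was seen, the arms move closer together.

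The primary objective (6.2) is to find outcomes that diverge between arms, so that a larger trial can be designed. Attenuation could hide a candidate outcome or shrink an effect used for planning. There is a smaller cost as well. Section 6.4 plans to compare baseline rSO2 ("room air and oxygen supplemented) to all collected clinical variables to assess for possibly significant associations"). If care depends on the value seen, that association partly reflects the care.

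**Working it through.** The plan has no figure to reproduce. The 100 subjects (1:1) come without power, effect size, standard deviation or event rate, and nothing is said about how often a baseline might alter care. The check is therefore mainly a comparison of sections.

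**1. Are the values available to be seen?** Yes. They are open in both arms (7.1, 7.2.2), in the operating room, before blinding (11.2.4.3).

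**2. Do the documents show that treating clinicians see them?** No. Section 10.3 names clinicians as open viewers only in the intervention group and after baseline. For controls the documents neither inform nor shield the team. Exposure is likely from the setting, but it is inferred.

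**3. Is a baseline informative by itself?** To some extent, on the protocol's own terms.
- Sections 7.4.1.1 and 7.4.1.2 analyse absolute rSO2 thresholds from 60% down to 20%.
- The Study Rationale in section 5 cites rSO2 below 65% in thoracic patients, with an odds ratio of 2.03 for early cognitive dysfunction. Its 95% interval, 0.74 to 5.59, includes 1.
- Section 6.4 compares baseline values with all clinical variables.

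**4. Can a baseline start the intervention?** No. Sections 7.1 and 10.3 trigger the algorithm at a fall of more than 20% from the oxygen-supplemented baseline. Section 7.2.3 defines a significant desaturation as a fall of 10% or more from the room-air baseline. Those passages must be reconciled as a separate matter, but both describe a fall from baseline. For an assumed baseline of 60%, the two boundaries would be 0.80 × 60 = 48% and 0.90 × 60 = 54%. Knowing the 60% does not tell a clinician whether a control has crossed either one, because the current value and trend are hidden.

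**5. Scale, under assumptions only.** Assume 50 per arm, two-sided 0.05, 80% power and a comparison of two means. The detectable standardized difference is (1.960 + 0.842) × √(2/50) = 0.56. Suppose exposure reduced a true difference of that size by a fraction f. Power with 50 per arm is then Φ(0.56(1 − f)/√(2/50) − 1.960), and the total needed for 80% power grows by 1/(1 − f)².

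| f (hypothetical) | 1/(1 − f)² | Power with 50 per arm | Total for 80% power |
|---|---|---|---|
| 0 | 1.00 | 80% | 100 |
| 5% | 1.11 | 76% | 112 |
| 10% | 1.23 | 71% | 124 |
| 20% | 1.56 | 61% | 158 |
| 30% | 2.04 | 50% | 206 |

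Totals are rounded up to whole subjects per arm. Nothing in the documents supports any row above zero. The table shows only how dilution would act if it occurred.

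**The case against.** The strongest reply is that the baseline is shared background. Both arms have it, on purpose and for a stated reason. The randomized contrast (6.1, 7.1) is open monitoring plus an algorithm against blinded monitoring. Care prompted equally in both arms by a common baseline leaves the difference as a fair estimate of what continuous display and the algorithm add. On this view, hiding control baselines only redefines the comparison.

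Much of this stands. Under the narrow contrast the estimate is not invalid. But section 5.1 asks about the impact of NIRS monitoring itself, and a team that has seen the baselines is not fully without monitoring information. The stated reason is readability, which does not need the treating team to see the numbers.

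Other points also stand. The team will know the arm once the display stays open or goes dark, so hiding the baselines removes only part of the performance bias. Section 11.3.2 already suggests that control rSO2 stays out of the anesthesia computer record. Evidence that clinicians would act on a baseline value is thin.

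A reader might infer that part of the intervention leaks into the control arm, or that the trial loses a definite share of its power. The documents support neither. The intervention needs a current reading to act on, controls have none on display, and no leakage fraction is given or can be derived.

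**Conclusion.** The gap is real but small. Control baselines are openly displayed before induction and no section shields the treating team, so clinicians may be exposed to information that the control arm is otherwise designed to withhold. The result is a modest performance-bias risk of unknown size, probably but not certainly toward no difference.

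This rests on two assumptions: that clinicians at the patient's side can see the console, and that some would act on an absolute baseline value. The first is likely from the setting; the second is plausible but undocumented. The risk does not undermine a 100-subject pilot. It merits a change because the change is nearly free and leaves the stated purpose of the open baseline intact.

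**What to change.** In sections 7.1, 7.2.2, 10.2 and 11.2.4, replace the open-baseline wording with the following, for both arms:

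- The research assistant alone views the room-air and oxygen-supplemented baselines, records them on the study data collection tool, and confirms that both sides are readable.
- The console is turned away from the treating clinicians during this step. It should not be covered, because sections 8.6 and 10.2 raise a concern about bias from a blinder fixed to the display.
- The assistant then activates electronic blinding in controls, or opens the display in the intervention arm.
- Control baseline values are not told to the care team.

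The readability check is kept, and no treatment rule or intervention step changes. The assistant is already present to time the oxygen baseline, so no staff are added. The costs are the protocol wording and the positioning of the console for a few minutes. If the sponsor prefers to keep open baselines, the plan should say who views them in controls and list the possible exposure as a limitation.
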